### 11.3. Analyses of Secondary Efficacy Endpoints

The secondary efficacy endpoints will be analyzed based on ITT population. Supportive analysis for the secondary efficacy endpoints will be analyzed in mITT population.

#### 11.3.1. Key Secondary Endpoint – Relapse-free Survival (RFS)

##### Primary analysis

Relapse-free survival is defined as the time from the date of randomization to the date of documented relapse or death from any cause, whichever occurs first. Subjects who are still alive without documented relapse, or who were lost to follow-up or withdrew consent without documented relapse, will be censored at the date of their last bone marrow assessment. Relapse is defined according to the IWG AML response criteria. See Appendix 17.7 for definitions of response categories. Documented relapse is defined as, the earliest date of the following

- $\geq 5\%$  bone marrow blasts (myeloblasts) from Central Pathology report, or
- appearance of  $> 0\%$  blasts in the peripheral blood with a later bone marrow confirmation (bone marrow blast [myeloblasts]  $\geq 5\%$ ) within 100 days, or
- at least 2 peripheral blasts  $\geq 5\%$  within 30 days.

Peripheral blasts reported from both Central Pathology and Central lab will be considered. Subjects who withdrew for any reason or received another therapy for AML without documented relapse will be censored on the date of their last bone marrow assessment, prior to receiving any other therapy for AML. Subjects who are still on treatment at the time of study closure without documented relapse will be censored on the date of their last bone marrow assessment. These rules are based on FDA guidance for cancer trial endpoints [REDACTED], and table 2 specifies the application of the guidance for various common situations for the calculation of RFS.

**Table 2** Primary Censoring Rules for RFS

Situation	Derivation Rules	Situation Outcome

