16. All concomitant over-the-counter medications, prescription medications, including anti-infectives for prophylaxis and/or treatment of an infection taken from Cycle 1, Day 1 up to 28 days after the last dose of IP or up to the Treatment Discontinuation visit, whichever period is longer, must be recorded on the appropriate page(s) of the CRF.
17. A bone marrow aspirate and biopsy should ideally be collected at Screening, no earlier than 14 days prior to randomization. The screening bone marrow aspirate and biopsy are required to be repeated even if a bone marrow aspirate and biopsy was performed for disease diagnosis/status as part of the standard of care within 28 days of Cycle 1, Day 1. The bone marrow aspirate slide, bone marrow biopsy slide, bone marrow aspirate sample for cytogenetics testing/chromosome analysis, and unstained peripheral blood smear slides must be sent to the central laboratory for review by the central pathology reviewer.

In addition, bone marrow aspirates must be collected during double-blind treatment phase on Day 1 (± 7 days) of Cycles 3, 6, 9, 12, 15, 18, 21, 24, 30, 36, and the Treatment Discontinuation visit, in order to confirm continued CR or CRi, relapse after CR or CRi (as assessed by the Investigator based on CBC with WBC differential results), or disease relapse. After Cycle 36 bone marrow assessment for disease relapse is performed only if clinically indicated. If disease relapse features are observed following a bone marrow aspirate, it is recommended that a repeat bone marrow aspirate be performed at least 3-4 weeks later to confirm disease relapse unless the blast count was greater than 50% in the marrow or peripheral blood. Additional aspirates may be collected if clinically indicated or required for toxicity assessment. A bone marrow biopsy can be collected in conjunction with an aspirate if it is standard institutional practice. A bone marrow biopsy may be needed to evaluate bone marrow cellularity. Whenever a bone marrow aspirate sample is sent to the local laboratory, additional (differently prepared) bone marrow aspirate slides must be sent to the central laboratory for review by the central pathology reviewer. Instructions for submission of bone marrow samples to the central (pathology) reviewer are provided in Study Reference and/or Study Central Laboratory Manual.

18. Bone marrow biopsies may be needed to assess bone marrow status if an adequate bone marrow aspirate cannot be attained.

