10.6.2. Secondary Efficacy Analyses

10.6.2.1. Key Secondary Efficacy Analyses

Relapse-free survival (RFS) is defined as the interval from the date of randomization to the date of documented relapse after CR or CRi or death from any cause, whichever occurs first. Subjects who are still alive without documented relapse after CR or CRi, or who were lost to follow-up without documented relapse, will be censored at the date of their last response assessment. Relapse after CR or CRi is defined according to the IWG AML response criteria ([Appendix E](#)).

The analysis of RFS will be performed using the ITT population and will be analyzed using the same methods as those used for the primary efficacy analysis of OS. The p-value from the stratified log-rank test will be the confirmatory p-value.

The analysis of the RFS endpoint will be repeated for the mITT-population as a supportive/exploratory analysis. Additional sensitivity analyses, based on the ITT population, will be performed using modified RFS definitions. For these analyses of RFS, subjects lost to follow-up without documented relapse or death will be 1) considered as having an event; and 2) considered as having an event if they were randomized to the azacitidine treatment group and censored if they were randomized to the placebo treatment group. The event/censoring time will be the date of the last response assessment.

In order to assess and compare the modified definition of AML relapse being used in this protocol as criteria for discontinuation from treatment (ie, appearance of > 15% blasts in the bone marrow or peripheral blood) with respect to the IWG definition of relapse after CR or CRi ([Appendix E](#)), an exploratory analysis based on the ITT population, will be performed for RFS using this modified definition of relapse. For this analysis of RFS, relapse after CR or CRi is defined as the appearance of > 15% blasts in the bone marrow or peripheral blood. Subjects who are still alive without documented relapse after CR or CRi or who were lost to follow-up without documented relapse will be censored at the date of their last response assessment. This exploratory modified RFS endpoint will be analyzed using the same methods as described above for the key secondary efficacy analysis.

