### 17.7. International Working Group AML Response Criteria

Hematologic Response According to IWG Criteria for AML	
Category	Definition
Morphologic Complete Remission (CR)	The following conditions should be met: 
 
• ANC > 1,000/<math>\mu</math>L;
 
• Platelet count <math>\geq</math> 100,000/<math>\mu</math>L;
 
• The bone marrow should contain less than 5% blast cells;
 
• Auer rods should not be detectable;
 
• No evidence of extramedullary disease;
 
• Independent of transfusions.
 

Morphologic Complete Remission with Incomplete Blood Count Recovery (CRi)	Defined as a morphologic complete remission but the ANC count may be < 1,000/ $\mu$ L or the platelet count may be < 100,000/ $\mu$ L.
Cytogenetic Complete Remission (CRc)	Defined as morphologic complete remission with a reversion to a normal karyotype.
Relapse Free Survival	Defined for patients who achieve CR/CRi, and is measured from the date of attaining leukemia free state until the date of AML relapse or death from any cause, whichever occurs first.
Disease Relapse	Relapse after CR/CRi is defined as reappearance of leukemic blasts in the peripheral blood or $\geq$ 5% blasts in the bone marrow not attributable to any other cause (eg, bone marrow regeneration after consolidation therapy). In the setting of recent treatment, if there are no circulating blasts and the bone marrow contains 5% to 20% blasts, a repeat bone marrow performed at least a week later is necessary to distinguish relapse from regeneration.

Source:

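### The RFS relapse rule scores a single central marrow with at least 5% blasts, without the cause exclusion and conditional repeat marrow in the IWG criteria it cites, and the SAP does not declare the departure

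*SAP*

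**What the plan says.** Protocol 10.6.2.1 sets the standard for RFS: "Relapse after CR or CRi is defined according to the IWG AML response criteria" (Appendix E). SAP 11.3.1 repeats it: "Relapse is defined according to the IWG AML response criteria", pointing to SAP 17.7, which carries the same text as Appendix E.

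SAP 11.3.1 then gives the working rule: "Documented relapse is defined as, the earliest date of the following". Three routes follow:

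- at least 5% "bone marrow blasts (myeloblasts) from Central Pathology report";
- any "blasts in the peripheral blood with a later bone marrow confirmation" of at least 5% within 100 days;
- two peripheral blast values of at least 5% within 30 days.

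SAP 17.7 attaches two conditions to relapse. Blasts must not have another explanation, and regeneration after consolidation is the example given. The second condition covers recently treated subjects whose marrow shows 5–20% blasts while none circulate. For them, "a repeat bone marrow performed at least a week later is necessary to distinguish relapse from regeneration".

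Protocol Table 1, footnote 17, tells sites that after relapse features on an aspirate "it is recommended that a repeat bone marrow aspirate be performed at least 3-4 weeks later to confirm disease relapse", except when blasts exceed 50%.

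The RFS p-value is confirmatory once OS has succeeded (SAP 11.1 and 11.3.1). Time to relapse (SAP 11.3.2) also rests on documented relapse.

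**The concern.** The marrow route is the only one of the three that needs no second observation. Take a hypothetical subject with 6% marrow blasts at Cycle 3, no circulating blasts, and 2% on the repeat aspirate that footnote 17 recommends. If treatment counts as recent, SAP 17.7 uses the repeat to separate relapse from regeneration. SAP 11.3.1 records an RFS event at Cycle 3, and because the earliest date governs, the 2% result cannot undo it.

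The circumstances are not remote. Subjects enter within 4 months (± 7 days) of first CR/CRi, with or without consolidation (Protocol 7.2). G-CSF is allowed in both arms (Protocol 8.1.2), and Protocol section 12 names myeloid growth factor as a non-relapse cause of blasts. Ten marrows are scheduled between Cycles 3 and 36.

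At stake is the key secondary endpoint, which would be measured under a definition that differs from the one it cites. OS is unaffected.

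**Working it through.** **1. Text comparison.**

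| Element | SAP 17.7 / Protocol Appendix E | SAP 11.3.1, first route |
|---|---|---|
| Marrow threshold | at least 5% | at least 5% |
| Other causes excluded | yes | not mentioned |
| Repeat marrow, 5–20% blasts, none circulating, recent treatment | necessary, at least a week later | not mentioned |
| Date | not specified | earliest |

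SAP section 15 lists two changes to the protocol's RFS analyses. Neither is this one.

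**2. Do other provisions cover the gap?**

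- Investigator-assessed RFS (SAP 11.3.1, sensitivity analysis): partly. Attribution to another cause can enter, but no repeat marrow is stated to be required.
- EMA-rule RFS (SAP Table 3): no. It changes censoring only.
- RFS with the higher blast threshold (above 15% in Protocol 10.6.2.1): dropped in SAP section 15.
- Third-party adjudication of central/local disagreement on CR/CRi status (Protocol 4.1): not carried into the SAP rule.

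**3. Size.** The documents contain no RFS event target or power and no rate of regenerating marrows, so there is no plan figure to reproduce. Everything below rests on assumptions: 230 per arm, exponential RFS, placebo median 6 or 10 months, marrows on Day 1 of the scheduled cycles, a constant probability of a false reading of at least 5% at each marrow while truly relapse-free, censoring uniform over 24–60 months, unstratified log-rank, and 400 simulated trials per row.

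True HR 0.70; cells show the mean estimated HR and power:

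| False rate per marrow, azacitidine / placebo | Median 6 months | Median 10 months |
|---|---|---|
| 0 / 0 | 0.704, 97.2% | 0.702, 96.8% |
| 1% / 1% | 0.712, 97.0% | 0.720, 92.8% |
| 3% / 3% | 0.725, 93.8% | 0.736, 89.8% |
| 2% / 1% | 0.739, 88.2% | 0.752, 83.0% |
| 3% / 1% | 0.775, 79.2% | 0.805, 61.2% |
| 5% / 1% | 0.823, 53.0% | 0.888, 24.8% |
| 1% / 2% | 0.692, 98.5% | 0.692, 97.2% |
| 1% / 3% | 0.686, 98.2% | 0.656, 99.0% |

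True HR 1.0; cells show the mean estimated HR and the one-sided rate of falsely favouring azacitidine (nominal 2.5%):

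| False rate, azacitidine / placebo | Median 6 months | Median 10 months |
|---|---|---|
| 0 / 0 | 1.000, 3.5% | 1.009, 1.5% |
| 3% / 3% | 1.003, 3.0% | 0.993, 2.5% |
| 1% / 2% | 0.981, 5.0% | 0.958, 7.2% |
| 1% / 3% | 0.947, 6.2% | 0.906, 18.0% |

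With 400 trials the standard error near 5% is √(0.05 × 0.95 / 400) = 1.1 percentage points, so only the larger excesses are clear.

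**4. Hand check.** False relapse adds roughly a constant hazard h to each arm, so the observed HR is about (0.70λ + h_A) / (λ + h_P). For a 6-month median, λ = ln 2 / 6 = 0.1155 per month. Marrows every three cycles are 84 / 30.4375 = 2.76 months apart, so 1% per marrow is h = 0.0036 and 3% is h = 0.0109.

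- 3% / 3%: (0.0809 + 0.0109) / (0.1155 + 0.0109) = 0.73.
- 3% / 1%: (0.0809 + 0.0109) / (0.1155 + 0.0036) = 0.77.
- 1% / 3%: (0.0809 + 0.0036) / (0.1155 + 0.0109) = 0.67.

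These agree with the simulation to within about 0.02.

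**The case against.** The strongest defence is that one reading by a pathologist blinded to treatment is objective and is applied identically to both arms. Repeat aspirates are only recommended, so a rule that depends on them lets the investigator's choice of testing influence event status. Under Protocol 8.2.6, escalation for blasts above 5% and up to 15% is optional, so a subject may stay on unescalated blinded drug. A true relapse that responds could then be erased as regeneration, perhaps mainly in the active arm. This stands. It is why rewriting the confirmatory rule is debatable and the single-marrow result should remain visible.

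It is also fair that entry requires less than 5% blasts and that the first on-study marrow comes about 8 weeks into treatment (Cycle 3 Day 1 is 2 × 28 = 56 days after Cycle 1 Day 1). Regeneration after consolidation becomes a less likely explanation at later visits. A constant error rate through Cycle 36 may therefore overstate the effect.

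Three stronger readings are tempting but unsupported.

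- A reader might infer that the IWG criteria always require a repeat marrow. They call it necessary only after recent treatment, with 5–20% marrow blasts and none circulating.
- A reader might infer that false relapses fall mainly on azacitidine because only that arm receives active drug. No passage says azacitidine cycles produce such marrows. The causes the protocol names, consolidation and growth factor, can apply in both arms.
- A reader might see a contradiction between at least one week (Appendix E) and at least 3–4 weeks (footnote 17). A marrow at 3–4 weeks satisfies both. The two texts differ in scope and have not been tied together, but they are not incompatible.

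**Conclusion.** The inconsistency is on the face of the SAP: the rule cites criteria, omits two of their conditions, and does not say so. Regeneration can be scored as relapse; the documents do not show that it is, or how often.

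Size and direction are unknown. On the assumptions above, equal error of 1–3% per marrow moves a true HR of 0.70 to 0.71–0.74, a small shift toward 1. An excess on azacitidine (2–5% against 1%) gives 0.74–0.89 and works against the drug. An excess on placebo (2–3% against 1%) gives 0.66–0.69 and, with no true effect, one-sided false-positive rates of about 5–18%. It would therefore be wrong to conclude either that the rule is safely conservative or that it favours azacitidine.

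The point deserves correction because RFS carries a confirmatory p-value and the pre-specified investigator-assessed analysis does not clearly resolve it. It does not touch the primary endpoint.

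**What to change.** 1. Reconcile SAP 11.3.1 with SAP 17.7 and Protocol Appendix E: either align the first route with the cited criteria, or list the departure and its reason in SAP section 15.
2. Before database lock, pre-specify an ITT RFS analysis, and the matching time-to-relapse analysis, with this rule. A central marrow with 5–20% blasts and no circulating blasts is not an event if a later central marrow shows less than 5% blasts. That later marrow must be taken at least 7 days afterwards (the SAP 17.7 minimum) and before any escalation for relapse or new AML therapy. Subjects with no repeat marrow still count as relapsed.
3. Report by arm how many RFS events rest on one unconfirmed 5–20% marrow, how many of those subjects had a repeat, and how many repeats were taken on continued study drug.
4. State how the repeat intervals in footnote 17 and Appendix E fit together.

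The cost is some SAP wording, one extra derivation and a short table. Footnote 17 already recommends the repeat aspirate and sends slides to central review, so no new procedure is needed. The drawback is that some subjects who respond on drug may be reclassified as not relapsed, so the single-marrow result should be shown alongside.

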**Sensitivity analysis**

The analysis of the RFS endpoint will be repeated for mITT population as a supportive analysis.

Additional sensitivity analysis, based on the ITT population, will be performed using the RFS definition where documented relapse is based on investigator assessed response.

In addition, sensitivity analysis of RFS using censoring rules based on EMA guidance [REDACTED]

[REDACTED] will also be performed. Details of the EMA censoring rule are provided in Table 3 below.

**Table 3** EMA Censoring Rules for RFS

Situation	Derivation Rules	Situation Outcome
Either documented relapse or death	Define event date is earliest of: 
 
• Date of documented relapse
 
• Date of death
 
	Event, Event date is earliest of documented relapsed date or death date.
Without documented relapse or death		Censor Censor date is date of last bone marrow assessment or date of randomization if no post-baseline bone marrow assessment

### 11.3.2. Additional Time-to-Event Secondary Efficacy Endpoints

Other time-to-event secondary efficacy endpoints will be analyzed similarly to the primary efficacy endpoint without stratification. Kaplan-Meier methods will be used to estimate time-to-event curves, unless otherwise specified.

#### **Time to relapse**

Time to relapse is defined as the time from the date of randomization to the date of documented relapse. Time to relapse will be analyzed using a competing risk analysis where death without documented relapse is treated as a competing risk for relapse. Similar censoring rules as in primary analysis of RFS will be applied. The cumulative incidence function ([REDACTED]) for time to relapse will be summarized and displayed graphically for each treatment arm.

### **Time to discontinuation from treatment**

Time to discontinuation from treatment will be assessed and is defined as the interval from the date of randomization to the date of discontinuation from IP. Subjects who are ongoing in treatment at the time of study closure will be censored at the date of last visit.

Time to discontinuation from treatment will be analyzed using a competing risk model with reason for treatment discontinuation classified as:

- Disease relapse
- Adverse event(s)
- Became eligible for bone marrow or stem cell transplant
- Withdrawal of consent / lost to follow-up / protocol violation /Other
- Death

Cumulative incidence curves will be estimated and summarized for each specific reason for discontinuation from treatment by treatment arm.

## **11.4. Subgroup Analysis**

In addition to analyses that include all ITT subjects, additional exploratory subgroup analyses will be performed where an adequate number of subjects are available in each subgroup to allow for meaningful interpretation of results. Analyses will be performed within the following subgroups for the OS and RFS endpoints:

- Age at induction therapy (< 65, ≥ 65, ≥ 75 years)
- Sex (male, female)
- Race (White, Asian, Black or Others)
- CR/CRi status at randomization (CR, CRi)
- CR/CRi status at first achieving response (CR, CRi)
- CR/CRi status at randomization and use of consolidation (CR with consolidation, CR without consolidation, CRi with consolidation, and CRi without consolidation)
- Prior history of MDS or CMML (yes, no)
- Cytogenetic risk category at induction therapy (intermediate, poor)
- MRD status at randomization (positive, negative)
- CR/CRi status at randomization and MRD status at randomization (CR with MRD positive, CR with MRD negative, CRi with MRD positive, and CRi with MRD negative)
- Consolidation therapy following induction (yes, no)
- Consolidation therapy following induction (1 or 2 cycles, 3 or 4 cycles)
- Geographic region (North America, Europe, Asia and Australia)
- ECOG performance status (0 or 1, 2 or 3)

[REDACTED]

## 12. SAFETY ANALYSIS

All analyses of safety data will be conducted using the safety population, which are subjects who received at least 1 dose of study drug. All safety summaries will be provided by treatment arms.

For summaries of safety data, the on-treatment period is defined as the period from date of first dose of IP through the date of last dose of IP plus 28 days, inclusive. Post-treatment period is defined as the period beyond the 28 days after the date of the last dose of IP.

By subject listings of all AEs, Treatment-emergent Adverse Events (TEAEs, as defined below in section 12.1), serious TEAEs, grade 3 or 4 TEAEs, TEAEs leading to study drug discontinuation, TEAEs leading to dose reduction, TEAEs leading to dose interruption, TEAEs leading to dose reduction and dose interruption, TEAEs leading to death, AEs during pre-treatment period, and all deaths will be provided.

### 12.1. Adverse Events

Adverse events (AEs) will be coded according to MedDRA, version 22. The severity of AEs will be assessed by the investigator according to the Common Terminology Criteria for Adverse Events (CTCAE) version 4.0. For any AE not listed in the CTCAE grading system, the severity of these events will be assessed by the Investigator using a 5-point scale: “Grade 1/Mild,” “Grade 2/Moderate,” “Grade 3/Severe,” “Grade 4/Life-threatening,” or “Grade 5/Death.” TEAEs with a missing severity will be presented in the summary table as a severity category of “Missing.” Relationship of AEs to investigational product by the investigator is documented on the eCRF. Adverse events that are missing the relationship to study medication will be presented in the summary table as “treatment-related”. The imputed values for relationship to study drug will be used for incidence summaries while actual values will be presented in data listings.

Treatment-emergent adverse events (TEAEs) include adverse events that started between the first dose date and 28 days after the last dose date of study treatment. Alternative definition of TEAEs will also be defined from first dose date to 28 days after the last dose date of study treatment, or date of start of subsequent AML therapy, whichever is earlier. This definition is employed to better differentiate the incidence of TEAEs between oral azacitidine and placebo without potential attenuation of differences due to events that occur in both arms due to subsequent therapies (that may have initiated prior to 28 days post last dose of study treatment).

Adverse events will be summarized by system organ class, preferred term, and treatment arm. Adverse event summaries will include frequency tables of:

- Summary of TEAEs;
- TEAEs;
- TEAEs by decreasing order of frequency of PT;
- TEAEs by decreasing order of frequency of system organ class;
- TEAEs with most frequent preferred terms ( $\geq 10\%$  in the oral azacitidine group);
- Any occurrence of TEAEs by cycle of onset;

- Any occurrence of TEAEs by cycle day of onset;
- First occurrence of TEAEs by cycle of onset;
- First occurrence of TEAEs by cycle day of onset;
- TEAEs by maximum severity;
- TEAEs with severity of grade 3 or 4;
- TEAE with severity of grade 1 or 2;
- TEAEs leading to death;
- TEAEs related to study medication;
- TEAEs related to study medication with severity of grade 3 or 4;
- TEAEs related to study medication leading to death;
- serious TEAEs;
- serious TEAEs by decreasing order of frequency of PT;
- serious TEAEs related to study medication;
- serious TEAEs with severity of grade 3 or 4;
- serious TEAEs related to study medication with severity of grade 3 or 4;
- TEAEs leading to study medication discontinuation;
- TEAEs leading to dose reduction of study medication;
- TEAEs leading to dose interruption of study medication;
- TEAEs leading to dose interruption and reduction of study medication;
- TEAEs by sex;
- TEAEs by age group (< 65, ≥ 65 to 75, and ≥ 75years);
- TEAEs by race group (White, Asian, Black or Others);
- TEAEs by ECOG performance status (0 or 1, 2 or 3)

Additionally, the incidence rate per 100 person-years will be summarized for all TEAEs and Grade 3 or 4 TEAEs by system organ class, preferred term, and treatment arm. The incidence rate per 100 person-years is calculated as  $(100*n)/T$ , where n is the number of subjects with the given AE at the system organ class or preferred term level, and T is total person-years of exposure. If a subject has multiple events with the same preferred term, then the time to the first event is used. For subject with no event, time to earlier of last dose + 28 days or death date is used.

Subjects with multiple events reported for the same preferred term will be counted only once per system organ class and preferred term level. For summaries by severity (CTCAE grade), subjects with multiple events at the preferred term level will be counted once and for the highest reported severity. For summaries by treatment cycle, subjects with multiple events reported with

a start date within the same cycle for the same preferred term will be counted once per system organ class level and preferred term level within the cycle.

In summaries of TEAEs related to study medication, if a subject reports multiple occurrences of the same AE, only the related occurrence will be summarized. Adverse events with missing relationship to study medication will be imputed as related to study medication.

Additional safety analysis may be performed, displayed and summarized, when deemed necessary.

To assess the safety profile among subjects who have dose escalation, defined as subjects who have at least one assigned dose of 300mg × 21/28 days, the following summary tables will be provided in subjects with dose escalation:

- First occurrence of TEAE by dose schedule period (300mg × 14/28days, 300mg × 21/28days);
- Any occurrence of TEAE by dose schedule period (300mg × 14/28days, 300mg × 21/28days);
- Exposure adjusted incidence rate of first occurrence of TEAE by dose schedule period (300mg × 14/28days, 300mg × 21/28days);
- Exposure adjusted incidence rate of any occurrence of TEAE by dose schedule period (300mg × 14/28days, 300mg × 21/28days);
- Any occurrence of TEAEs by cycle of onset

The first occurrence and any occurrence of Grade 3/4 TEAE by dose schedule period will also be summarized.

